11.3 Multiplicity control and adjustment of error probabilities

The family-wise Type I error rate will be controlled in a hierarchical fashion in support of demonstrating superiority of the investigational device.

The primary endpoints will be evaluated in a fixed sequence, where the first null-hypothesis must be rejected at a 5% significance level (alpha 0.05) before proceeding with the next.

11.4 Analysis of the primary endpoint

- Residual volume at first flow-stop, will be analysed in a general linear mixed model with subject included as a random component. Evidence of superior effect will be concluded, if the 95% confidence interval of the difference between comparator and investigational device, do not include zero.
- Number of flow-stop episodes will be analysed, in a generalized linear mixed model, with subject included as a random component. Evidence of superior effect will be concluded, if the lower 95% confidence limit of the risk ratio between comparator and investigational device, is more than 1.

The models will include following fixed effects.

- Visit (visit 2 and 3 of catheterisation)
- Device (comparator and investigational device)

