11.2 Definition of analysis populations

Screening Failures (SF), Intention to Treat (ITT), Full Analysis Set (FAS), Safety and Per Protocol (PP) analysis set will be defined at a formal data review meeting prior to database lock. As a minimum, the data manager, the clinical manager, and the statistician will be involved in the classification of subjects.

Subjects not adhering to inclusion and/or exclusion criteria are considered screening failures (SF) and are not randomised.

The Safety population will constitute all subjects enrolled i.e., subjects who have given informed consent.

The ITT population will constitute all randomised subjects.

The full analysis set is a modified ITT population i.e., a sub-population of the ITT population, and will constitute all randomised subjects, who have been exposed to at least one device, with at least one endpoint recorded (data non-missing).

The PP is a sub-population of the full analysis set where all subjects have received treatment as per protocol.

Individual endpoints/data points may be excluded from the analysis, even though the corresponding subject belongs to any of the pre-defined populations. Exclusion of subjects or data points must be documented.

All statistical analysis and test of hypothesis will be based on the full analysis set, and in addition, Primary and Secondary endpoints will also be analysed in the PP population, if the PP population differs from the full analysis set. whereas adverse events and device deficiencies will be assessed in the safety population.

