11.8 Sample size

Input for the sample size calculations i.e., frequencies, rates, means and standard deviations are based on three exploratory studies CP322, CP323 and CP324. The studies investigated earlier prototypes of the micro-hole zone catheter with identical or similar endpoints in populations of both IC users and healthy volunteers.

A sample size for the primary endpoint of residual urine at 1st flow stop (RV1) is judged to be accommodated by 30 subjects with a power above 90%, assuming a difference of 40 mL, a $sd_{comparator}$ of 50 mL and a sd_{active} of 10 mL. (please see table 11-1). Taken into consideration a discontinuation of 20%, the endpoint of RV1 is sufficiently supported by randomising at least 36 subjects.

For primary endpoint of flow stop episodes a sufficient sample size is judged to be accommodated by 35 subjects with a power above 90%, assuming a difference of 1 flow stop with a $\lambda_{comparator}$ of 2 flow stop, and a λ_{active} of 1 flow stop (please see table 11-2). Taken into consideration a discontinuation of 20%, the endpoint of RV1 is sufficiently supported by randomising at least 42 subjects.

Aiming for an acceptably narrow 95% confidence interval, for the difference in frequency of positive haematuria events, sufficient inference is judged to be accommodated with 60 subjects completing the study (please see table 11-3). Taken into consideration a discontinuation of 20%, the aim is to randomise at least 72 subjects.

72 subjects should at least be randomised in support of the secondary endpoint of positive haematuria frequency and a sub-set of subjects, at least 42, should be randomised in support of the primary endpoints RV1 and number of flow stop episodes.

Table 11-1 Sample size calculation of Residual urine at 1st flow stop in a cross-over design, solving for varying power and number of subjects, assuming no within subject correlation as a worst-case approach, using proc Power in SAS.

μ (sd) comparator	μ (sd) active	Alpha	Power	Sample size
50 (90)	10 (15)	0.05	86.0 %	25
50 (90)	10 (15)	0.05	90.0 %	28
50 (90)	10 (15)	0.05	91.6 %	30

Table 11-2 Sample size simulation of Flow stop events in a cross-over design, solving for varying power and number of subjects, assuming no within subject correlation as a worst-case approach, using a generalised linear mixed model with proc Glimmix in SAS.

λ comparator	λ active	Alpha	Power	Sample size
2	1	0.05	81.2 %	25
2	1	0.05	88.0 %	30
2	1	0.05	92.2 %	35

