11.9 Level of significance and power

A significance level of alpha 0.05 (2-sided) will be applied.

The power for concluding superiority of the investigational device is at least 90% or higher.

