11.10 Pass/fail criteria

To demonstrate superiority of the investigational device, the null hypothesis of the primary endpoints must be rejected, at a 5% significance (alpha 0.05).

The pass criteria for the study are based on the results from analysing the two primary endpoints in a hierarchical fashion: rejecting the null-hypothesis on the first endpoint (Residual urine at first flow-stop) before continuing to the second (Number of flow-stop episodes).

12 Data management

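### The RV1 model sets no device-specific variance although the plan expects SDs five to six times larger on the comparator; the deciding confidence interval is miscalibrated if one-period data fall mostly on one device

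*Combined protocol and SAP*

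**What the plan says.** - **Model (11.4).** RV1 "will be analysed in a general linear mixed model with subject included as a random component". The fixed effects are device and "Visit (visit 2 and 3 of catheterisation"). The text gives no variance by device, no robust standard error and no degrees-of-freedom method.
- **Decision rule (11.4, 11.9, 11.10).** Superiority on RV1 is concluded "if the 95% confidence interval of the difference between comparator and investigational device, do not include zero". "A significance level of alpha 0.05 (2-sided) will be applied". RV1 is the first gate: the pass criteria require "rejecting the null-hypothesis on the first endpoint (Residual urine at first flow-stop) before continuing to the second".
- **Expected spread (11.8).** The text assumes a 40 mL difference with "a $sd_{comparator}$ of 50 mL and a sd_{active} of 10 mL". Table 11-1 has means of 50 and 10 and SDs of 90 and 15, with no within-subject correlation.
- **Analysis set (11.2).** Hypotheses are tested in the full analysis set, which takes randomised men "who have been exposed to at least one device, with at least one endpoint recorded (data non-missing"). Single data points may also be excluded, so one-period data can arise without withdrawal.
- **Losses (11.8).** A 20% discontinuation turns 35 men into 42 for the primary endpoints, an allowance of 7.

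**The concern.** The expected SD ratio is 50/10 = 5 or 90/15 = 6, so the variance ratio is 25 or 36. When every man has both values, the device contrast is a within-man difference. Its standard error then depends only on the spread of the differences, and unequal device variances do no harm.

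A man with one value is handled differently. A single-variance model gives his value an average precision: a comparator value is treated as more precise than it is, and a test value as less precise. If such values pile up on one device, the model's standard error no longer matches the true one. Because the interval for RV1 opens or closes the first gate, the 5% error rate, or the power, would then differ from what the plan states.

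**Working it through.** **The plan's own figure.** Table 11-1 gives 86.0%, 90.0% and 91.6% power at 25, 28 and 30 subjects. A paired test with zero correlation has SD of differences √(90² + 15²) = 91.2. At n = 30 the noncentrality is 40/(91.2/√30) = 2.40 and the power is 64.1%; at 25 and 28 it is 55.7% and 60.9%. The table is matched closely only by an unequal-variance two-sample test with twice the listed number per device (50, 56, 60): 86.0%, 89.7%, 91.7%. That discrepancy is a separate matter; only the table's SDs are used below.

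**Closed form, SD 90/15, zero correlation, ignoring the visit effect.** Let n_C and n_T be the numbers of comparator and test values.

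- Pooled variance: s² = (n_C·90² + n_T·15²)/(n_C + n_T).
- Model SE: √[s²(1/n_C + 1/n_T)].
- True SE: √(90²/n_C + 15²/n_T).

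| Values (comparator / test) | s² | Model SE | True SE | Ratio |
|---|---|---|---|---|
| 42 / 42 | 4162.5 | 14.08 | 14.08 | 1.00 |
| 35 / 42 (seven test-only men) | 3804.5 | 14.12 | 15.39 | 0.917 |
| 42 / 35 (seven comparator-only men) | 4520.5 | 15.39 | 14.12 | 1.090 |

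In a normal approximation the two-sided type I error is 2[1 − Φ(1.96 × ratio)]: about 7.2% at 0.917 and 3.3% at 1.090.

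**Simulation of the 11.4 model with one residual variance.** Settings: REML, random subject, fixed visit and device, 42 men, 21 per sequence, normal data, no true difference, and seven men with a V2 value only. For SD 90/15 and zero correlation, type I error by split of the seven was:

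| Test-only / comparator-only | Type I error |
|---|---|
| 0 / 7 | 3.6% |
| 1 / 6 | 3.9% |
| 2 / 5 | 4.5% |
| 3 / 4 | 4.9% |
| 4 / 3 | 5.6% |
| 5 / 2 | 5.8% |
| 6 / 1 | 6.6% |
| 7 / 0 | 7.0% |

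The average over random (binomial) splits is 5.2%. Across SDs of 90/15 and 50/10 and correlations of 0, 0.3 and 0.6:

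- All 42 complete: 4.8 to 5.4%.
- Splits of 3/4 or 4/3: 4.4 to 5.6%.
- Average over random splits: 4.9 to 5.2%.
- Seven test-only: 6.9 to 7.7%, coverage about 93%. For SD 90/15 and zero correlation the mean model SE is 14.1 against a true 15.5.
- Seven comparator-only: 3.3 to 3.7%, coverage about 96.5%. The corresponding SEs are 15.3 and 14.3.
- Fewer test-only men and no comparator-only men (SD 90/15, correlation 0.3): 6.5% with five, 5.4% with three.

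Monte Carlo error is about 0.3 to 0.4 points in the larger cells (10,000 to 20,000 runs) and 0.7 points in the smaller ones (4,000). Two smaller sets of runs (2,300 and 1,500) gave 7.5% and 7.9% for seven test-only men, and 4.2% and about 3.6% for seven comparator-only men.

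**Control.** With equal SDs and the same lopsided losses, type I error is 4.8 to 5.0%. The unequal variance is therefore the cause, not the imbalance alone.

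**With the variance allowed to differ by device.**

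- Separate variances plus a free covariance: 4.8 to 5.5% with seven test-only men, 4.5 to 5.2% with seven comparator-only men.
- Random subject plus a residual grouped by device: 5.1 to 5.5% (1,500 runs per cell, SD 90/15, correlation 0 and 0.3).
- Power at a 40 mL difference (SD 90/15, zero correlation), one variance to separate variances: 78% to 72% with test-only men, where the 78% comes from an interval that is too narrow; 73% to 79% with comparator-only men. With SD 50/10 it exceeds 99% under either model.

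**The case against.** A reader might infer that the interval is wrong as soon as anyone is left with one period. The documents do not support that: the interval holds with complete data and with roughly even splits, and random splits average to nominal.

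The 7 to 8% figure is also a corner case. All seven men would have to be lost after V2 and all from the test-first sequence. If loss is unrelated to sequence, that has probability C(21,7)/C(42,7), about 0.4%. The 20% in 11.8 is total discontinuation, and men lost before V2 contribute no RV1 value.

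The direction may be harmless. Test-first men return in T2 to a catheter type they already use, while comparator-first men meet the new device then. If unfamiliarity drives withdrawal, comparator-only values remain and the error is conservative. The per-protocol analysis, if limited to men with both periods, is unaffected.

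A single residual variance is an inference too, since 11.4 is silent on residual structure. Finally, a random subject effect with grouped residuals caps the implied correlation at 15/90 = 0.17, and one set of runs put its SE about 4% low with seven comparator-only men.

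Most of this stands, and it limits the size of the point. Two parts do not remove it. Balance cannot be assumed in an open-label trial where the home comparator is the man's own catheter. And despite the cap, the grouped-residual model held 5.1 to 5.5% at correlations of 0 and 0.3; an unstructured covariance has no such cap.

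**Conclusion.** The point holds in a conditional form. The plan predicts a five- to six-fold difference in SD, can keep one-period men in the set that decides the first gate, and specifies no device-specific variance. The interval is close to nominal when pairs are complete or one-period losses are balanced by device. When those losses fall mostly on one device, it is too narrow with test-only data (type I error up to about 7 to 8% at 7 of 42) or too wide with comparator-only data (about 3.5 to 4%). The direction cannot be known in advance.

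This does not show that the planned interval is wrong whenever men are lost, nor that the plan has written down a wrong model.

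The figures assume normal data, 1:1 sequences (the ratio is not stated), losses unrelated to outcome and seven men lost after V2. They also take one residual variance as the ordinary reading of 11.4. The result is similar for either pair of SDs in 11.8.

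**What to change.** In 11.4, and for self-catheterisation RV1 in 11.6 (which copies the primary model), specify a separate residual variance per device: either random subject with the residual grouped by device, or an unstructured covariance across the two devices. State Kenward-Roger degrees of freedom. Keep the estimate (the mean difference in g), the 95% confidence interval rule and the hierarchy.

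The cost is one sentence of analysis text, one model option and one more variance parameter to estimate. No further data or subjects are needed. The choice should be fixed before the data are seen, because which model favours the test device depends on which sequence loses men.

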11.5 Analysis of the secondary endpoints

- Red blood cell concentration will be analysed in a general linear mixed model with repeated measurements where subject and subject*device are included as random components. Evidence of superior effect will be concluded, if the 95% confidence interval of the difference between comparator and investigational device, do not include zero.
- Frequency of positive haematuria events will be analysed, in a generalized linear mixed model with repeated measurements, where subject and subject*device will be included as random components. Evidence of superior effect will be concluded, if the lower 95% confidence limit of the odds ratio between comparator and investigational device, is more than 1.

The models will include following fixed effects.

- Visit (visit 2 and 3 of catheterisation)
- Device (comparator and investigational device)

11.6 Analysis of supportive and explorative endpoints

Assessments and Endpoints pertaining to

- Residual volume at 1st flow-stop (RV1) (self-catheterisation)
- Pressure measurement at 1st flow-stop (self-catheterisation)
- Average residual volume post catheterisation
- Discomfort at insertion, emptying and withdrawal
- QoL Index score (Qualiveen questionnaire)

Will be analysed by a general linear mixed model identical to the model specified for the primary endpoint.

Endpoints pertaining to

- Number of flow-stops (self-catheterisation)
- Perception questions evaluated on a 5-point ordinal scale

Will be analysed by a generalized linear mixed model identical to the model specified for the primary endpoint.

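### Section 11.6 assigns the five-point perception items the flow-stop count model; taken literally, its variance is wrong for ordinal scores and its tests usually lose much of their power

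*Combined protocol and SAP*

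**What the plan says.** Section 11.6 has two lists. The first (residual volume, pressure, discomfort, quality-of-life index) receives the general linear mixed model used for RV1. The second holds two endpoints: the number of flow stops at self-catheterisation, and "Perception questions evaluated on a 5-point ordinal scale". For this second list the plan says: "Will be analysed by a generalized linear mixed model identical to the model specified for the primary endpoint".

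Section 11.4 gives only one generalized linear mixed model for a primary endpoint: "Number of flow-stop episodes will be analysed, in a generalized linear mixed model, with subject included as a random component". Visit and device are the fixed effects. Superiority is concluded if "the lower 95% confidence limit of the risk ratio between comparator and investigational device, is more than 1". No distribution or link is named, but Table 11-2 in Section 11.8 describes the endpoint by rates (lambda 2 against 1) and refers to a simulation "assuming no within subject correlation as a worst-case approach, using a generalised linear mixed model with proc Glimmix in SAS".

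The plan gives no ordinal model, score coding or effect measure for the perception items. Each Part I item in Appendix A also has a sixth box, 'Don't know' or 'Not applicable (lack of sensation)', with no analysis rule.

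**The concern.** A count model and a five-point item do not fit together, for three reasons.

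- **Variance.** A Poisson model sets the variance equal to the mean, about 3 to 4 for items scored 1 to 5 with central or favourable answers. A bounded item with an SD of 0.7 to 1.3 has a variance of about 0.5 to 1.7. A random subject effect can add variance to the model but cannot remove it, so the misfit stays.
- **Effect measure.** A ratio of mean category codes depends on arbitrary numbering. Means of 4 and 3 on a 1-5 coding give 4/3 = 1.33; the same answers coded 0-4 give 3/2 = 1.5.
- **Direction.** Appendix A mixes items where agreement is favourable (satisfied with the catheter) with items where it is unfavourable (resistance during withdrawal). The Section 11.4 rule, comparator over investigational above 1, cannot signal benefit for both under one coding.

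Catheter perception is one of the two parts of the exploratory objective (Section 4.3), and all subjects provide these data (Section 6.1). An over-wide interval could be misread as showing no difference between catheters.

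**Working it through.** **Step 1. Is the reference model Poisson?** Inputs from Sections 11.8 and 11.9: rates 2 and 1, two-sided alpha 0.05, no within-subject correlation. For a Poisson log rate ratio, SE = sqrt((1/2 + 1/1)/n) = sqrt(1.5/n), and power = Phi(ln 2/SE − 1.96).

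| n | SE | ln 2/SE − 1.96 | Power | Table 11-2 |
|---|---|---|---|---|
| 25 | 0.245 | 0.870 | 80.8% | 81.2% |
| 30 | 0.224 | 1.140 | 87.3% | 88.0% |
| 35 | 0.207 | 1.388 | 91.7% | 92.2% |

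All three agree within one percentage point. The model behaves as Poisson with a log link. This is an inference, because the plan names no distribution.

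**Step 2. Standard error on 1-5 scores.** With n pairs, the Poisson SE of the log ratio is sqrt(2/(n × mean)). The actual SE is approximately sqrt(2 × SD² × (1 − rho)/n)/mean. Their ratio is sqrt(mean)/(SD × sqrt(1 − rho)), and n cancels. For a symmetric item with mean 3.00, SD 1.10 and rho 0, this is 1.732/1.10 = 1.57; simulation gave 1.59.

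**Step 3. Range over response patterns.** The documents give no response distributions or correlations, so all of these are assumptions. Simulation used 60 completers and answers generated from a correlated latent normal, with latent correlation 0 to 0.7.

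| Pattern, coded 1-5 | Mean | SD | Model SE / true SE |
|---|---|---|---|
| Tightly clustered, favourable | 4.2 | 0.65 | 3.1 to 4.7 |
| Favourable (2/5/13/50/30%) | 4.0 | 0.90 | 2.2 to 3.6 |
| Skewed high | 4.05 | 1.07 | 1.9 to 3.0 |
| Symmetric (10/20/40/20/10%) | 3.0 | 1.10 | 1.6 to 2.7 |
| Low scores | 2.1 | 1.18 | 1.3 to 2.1 |
| Uniform | 3.0 | 1.41 | 1.2 to 2.1 |
| U-shaped | 3.0 | 1.64 | 1.0 to 1.7 |

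With 0-4 coding the range is 0.85 to 4.1. In a few settings the SE is then slightly too small, and type I error reaches 9%.

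**Step 4. Power of the fitted mixed models.** Both models had visit, device and a random subject effect, with 60 completers, 1-5 coding, an assumed latent shift of 0.4 SD and 200 data sets per setting. The Poisson random-intercept variance collapsed to about zero.

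| Pattern | Correlation | Poisson | Cumulative logit |
|---|---|---|---|
| Favourable | 0 | about 0% | about 52% |
| Favourable | 0.5 | about 0% | about 74% |
| Symmetric | 0 | 11% | 54% |
| Symmetric | 0.5 | 4.5% | 79% |

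Rejection under no difference was 0% for Poisson and 4.5 to 9% for cumulative logit (likelihood-ratio test). With 200 runs, the Monte Carlo SE at 5% is sqrt(0.05 × 0.95/200) = 1.5 percentage points. The upper figure may therefore reflect some excess of the likelihood-ratio test, and the cumulative-logit powers are approximate.

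**The case against.** The strongest defence is that 'identical' covers only the effects structure: random subject, fixed visit and device. Section 11.6 uses parallel wording for discomfort, pressure and quality of life, which are on different scales. It also calls the perception items ordinal, and the class of generalized linear mixed models includes the cumulative logit. This reading is possible. But Section 11.5 shows that where the outcome type changes, to binary haematuria, the plan writes out a separate model with an odds ratio. Section 11.6 makes no such change and puts the items beside a count. Even on the generous reading, the distribution, link and effect measure for these items are missing.

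A reader might also infer stronger conclusions that the documents do not support:

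- *That the standard errors are several times too wide as a fixed result.* The inflation depends on response pattern, correlation and coding, none of which the plan states. For category probabilities 0.03/0.10/0.22/0.40/0.25 (mean 3.74, SD 1.04) it is 1.87 at zero correlation and 2.64 at 0.5. Values of 4 or more need tightly clustered, highly correlated answers.
- *That the analysis would almost never detect a difference.* For those same probabilities, 60 pairs and zero correlation, power is about 5% against 62% for a paired t-test on scores at a cumulative odds ratio of 2.2, but about 17% against 87% at an odds ratio of 3. For a U-shaped item at zero correlation and a 0.4 SD shift, it is 41% against 50%.
- *That type I error is always near zero.* This fails for some patterns coded 0-4.

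Section 11.1 also provides for counts and percentages of discrete variables by device, so the raw answers may be visible whatever model is fitted.

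**Conclusion.** The point holds in a limited form. Section 11.6, followed as written, applies the flow-stop count model to ordinal items. If that model is Poisson with a log link, as Table 11-2 indicates, it has the wrong variance and an uninterpretable ratio. Its standard errors are then commonly about 1.5 to 3.5 times too large on 1-5 scores (full range about 1.0 to 4.7), so its tests are usually conservative and lose much of their power. The size rests on assumed response distributions, correlations, score coding, a 0.4 SD shift and 60 completers. The Poisson form is itself an inference.

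The items are exploratory, outside the fixed sequence in Section 11.3 and the pass criteria in Section 11.10. Primary and secondary conclusions are unaffected. The plan should still be corrected, because an exploratory null result from this model would be uninformative.

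**What to change.** In Section 11.6:

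1. Keep the count model for self-catheterisation flow stops only.
2. Analyse each five-point perception item with a cumulative-logit (proportional odds) mixed model, with visit and device as fixed effects and subject as a random effect. Report the common odds ratio with its 95% confidence interval.
3. State the direction of each item, so that it is clear which side of 1 favours the investigational catheter.
4. Exclude 'Don't know' from the ordinal scale. Report 'Not applicable (lack of sensation)' separately, because it describes a patient's condition rather than a missing opinion.

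The cost is a few sentences and a different distribution and link in the same SAS procedure, with no new data, visits or subjects. There is a small downside: proportional odds must be checked, and with about 60 completers sparse categories may need pooling. The pooling rule should be written in advance.
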